10.4.3. Pharmacokinetic Analyses

All safety analyzes will be performed on the PK Population.

Endpoint	Statistical Analysis Methods
Primary	There is no primary pharmacokinetic analysis.
Secondary	The serum GSK3772847 levels from this study will be summarised by treatment and nominal time.
	Further details will be described in the report and analysis plan.

10.4.4. Pharmacodynamic Analyses

All pharmacodynamic analysis will be described in reporting and analysis plan.

10.4.5. Other Analyses

PK, pharmacodynamic, and biomarker exploratory analysis will be described in the reporting and analysis plan. Any population PK analysis and pharmacodynamic analysis will be reported separately from the main clinical study report (CSR). Should a genetic/PGx analysis be performed, a separate reporting and analysis plan will be generated (See Appendix 6: Genetics).

10.4.6. Interim Analyses

Formal analyses will be performed at two timepoints.

End of Treatment Phase Analysis:

This will take place after all participants have completed the Week 16 visit. The data will be cleaned, the treatments unblinded and all clinic visits up to and including week 16 frozen. However, whilst no further efficacy data will be collected post week 16, due to an inability to lock log forms used for collection of exacerbation data, the end of treatment phase analysis will be considered an interim analysis for both efficacy and safety. Any safety data collected for participants who have completed clinic visits after Week 16 will also be cleaned and included in the analysis.

There will be no modifications to dosing regimens, sample size or any other aspects of the trial based on this data, as all study assessments, apart from follow-up, will have already been completed. As such an Independent Data Monitoring Committee (IDMC)

207597

will not be used, as no further investigational product will be prescribed after this analysis has taken place.

Final Analysis:

This will take place after all subjects have completed the study. Data for visits after Week 16 as well as data collected on log pages will be cleaned and the database frozen. This will be the final analysis for the study.

The Reporting and Analysis Plan will describe the planned analyses in greater detail.

Instream review:

An iSRC will periodically review unblinded safety data to protect and maintain participant safety whilst maintaining scientific validity. Members of the iSRC will be independent of the project. The data will include, but not necessarily be limited to SAEs, Holters and ECGs. Details are described in the Charter.

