4. OBJECTIVES AND ENDPOINTS

	Objectives	Endpoints
Pri	mary	
•	To evaluate the efficacy of GSK3772847, compared with placebo, administered intravenously every 4 weeks for 12 weeks (Week 0 – Week 12, 4 doses in total) in participants with moderately severe asthma.	Primary – Proportion of participants with loss of asthma control over Weeks 0-16 where 'loss of asthma control' is defined as at least one of the following: • Asthma Control Questionnaire (ACQ-5) score increase from baseline (measured at the end of Run-in) ≥0.5 point or • Pre-bronchodilator Forced expiratory volume in 1 second (FEV1) decrease from baseline (measured at the end of Run-in) >7.5 % or • Inability to titrate inhaled corticosteroid according to the pre-defined schedule (Section 5.1) or • A clinically significant asthma exacerbation (requiring oral corticosteroid [OCS] and/or hospitalisation).
Sec	condary	
•	To evaluate other aspects of efficacy of GSK3772847 compared with placebo in participants with moderately severe asthma.	 Other efficacy endpoints (at or by Week 16): Proportion of participants with a ≥0.5 point. ACQ-5 score increase from baseline. Proportion of participants who have prebronchodilator FEV1 decrease from baseline (measured at the end of Run-in) >7.5 %. Proportion of participants where inhaled corticosteroids (ICS) cannot be titrated in accordance with the pre-defined schedule. Proportion of participants who have a significant asthma exacerbation (requiring OCS and/or hospitalisation).

Objectives	Endpoints

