9.2. Adverse Events

The definitions of an AE or SAE can be found in Appendix 4.

Asthma exacerbations or worsening of asthma should not be recorded as an AE, unless they meet the definition of an SAE. For the purposes of this study, asthma exacerbations

will be collected and recorded on the exacerbations log in the eCRF. The treatment details must also be recorded in the eCRF. The time period for collection of asthma exacerbations will begin from screening and will end after the follow-up period has been completed.

The investigator and any designees are responsible for detecting, documenting, and reporting events that meet the definition of an AE or SAE and remain responsible for following up AEs that are serious, considered related to the study treatment or the study, or that caused the participant to discontinue the study treatment (see Section 8).

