10.4. Statistical Analyses

10.4.1. Efficacy Analyses

All efficacy analyses will be performed on the mITT Population.

Endpoint	Statistical Analysis Methods
Primary	The primary endpoint proportion of subjects with loss of asthma control will be analyzed using both Bayesian and Frequentist methods. A subject is deemed to have met the endpoint of loss of asthma control if they meet the criteria for any of the components of the definition of loss of asthma control.
	The posterior probabilities that the ratio of the proportion of subjects with loss of asthma control on GSK3772847 compared with placebo is less than 1.0, 0.75, 0.5 and 0.2 (i.e. a 0%, 25%, 50% and 80% reduction) will be calculated analytically assuming a non-informative prior. This will be supported by an estimate of the ratio with a 95% credible interval. Results will also be presented for the two eosinophils strata separately.
	In addition, the proportion of participants with loss of asthma control will be analyzed using logistic regression allowing for baseline eosinophils strata. The odds ratio, 95% CI and p-value for the comparison of GSK3772847 with placebo will be presented.
	Results will also be presented for the two eosinophils strata separately by fitting a separate model with an additional term for eosinophil strata by treatment interaction. The effect of eosinophils as a continuous covariate will also be examined in a separate-logistic regression model.
	 Missing data will be handled using the following methods: 1) The loss of asthma control will be set to missing for participants who withdraw from IP prior to Week 16 for reasons other than loss of asthma control 2) A sensitivity analysis will be performed where participants who withdraw from IP prior to Week 16 for reasons other than loss of asthma control will have the endpoint set to loss of control
Secondary	The following secondary endpoints will be analyzed using the same statistical analysis as described for the primary endpoint: • Proportion of participants with a clinically significant asthma exacerbation

Endpoint	Statistical Analysis Methods
	 (requiring OCS and/or hospitalisation) Proportion of participants with Pre-bronchodilator FEV1 decrease from Baseline (measured at the end of Run-in) >7.5 % Proportion of participants with Inability to titrate inhaled corticosteroid

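### Treatments are unblinded after Week 16 while the exacerbation log, which feeds the primary endpoint, is still unlocked, so Week 0–16 entries can change after unblinding

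*Protocol*

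**What the plan says.** Protocol Section 4 defines the primary endpoint as loss of asthma control over Weeks 0–16. It has four components; one is a clinically significant exacerbation, meaning one that needs oral corticosteroids or hospital admission. Section 10.4.1 makes any single component sufficient: "A subject is deemed to have met the endpoint of loss of asthma control if they meet the criteria for any of the components".

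Under Section 9.2, exacerbations "will be collected and recorded on the exacerbations log in the eCRF". The same section keeps that log open well past the endpoint window: "The time period for collection of asthma exacerbations will begin from screening and will end after the follow-up period has been completed". In the Schedule of Activities the last follow-up visit is at Week 28.

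Section 10.4.6 plans two analyses. At the first, after all participants have completed Week 16, "The data will be cleaned, the treatments unblinded and all clinic visits up to and including week 16 frozen". The log is the exception, "due to an inability to lock log forms used for collection of exacerbation data", and for that reason "the end of treatment phase analysis will be considered an interim analysis for both efficacy and safety". The second, named as the final analysis, follows study completion: "Data for visits after Week 16 as well as data collected on log pages will be cleaned and the database frozen".

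**The concern.** Data that decide the primary result are normally fixed before anyone who can influence them learns the treatment codes. For the visit-based data the protocol does this. For the exacerbation log the stated order is to unblind first and freeze later. Onset date, oral corticosteroid use and hospital admission for an event before Week 16 all sit on a form that stays editable across the unblinding.

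What is at stake is the final primary result, because the final analysis is run on the log as it stands at the later freeze. The same applies to the secondary endpoints of exacerbation, of exacerbation or inability to titrate, and of time to loss of control. Nobody need act in bad faith for this to matter. Queries raised, or not raised, by people who know the allocation and the first result are enough to make the final version open to challenge.

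**Working it through.** The point disputes no figure in the protocol. The check has two parts: whether the sequence is as described, and how far a small change could move the result.

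**Sequence**

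1. An exacerbation alone makes a primary event (Sections 4 and 10.4.1).
2. Exacerbations are held on an eCRF log that runs to the end of follow-up (Section 9.2).
3. At the Week 16 analysis the data are cleaned, treatments are unblinded and clinic visits are frozen. The log is not locked (Section 10.4.6).
4. Log pages are cleaned and frozen at the final analysis (Section 10.4.6).

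Step 3 speaks of cleaning in general terms, so a first clean of the log before unblinding is possible. Steps 3 and 4 together still leave entries with onset up to Week 16 editable after unblinding. Section 10.4.6 fixes no cut-off or snapshot for those entries and does not say who learns the codes.

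**Planning figures**

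Section 10.2 assumes 70 evaluable per arm and 44% against 22%, with 80% power. The uncorrected two-proportion test reproduces this:

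z = (|p1 − p2|·√n − 1.96·√(2·p̄·(1 − p̄))) / √(p1(1 − p1) + p2(1 − p2))

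= (0.22·√70 − 1.96·√(2·0.33·0.67)) / √(0.2464 + 0.1716)

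= (1.841 − 1.303) / 0.647 = 0.83, so power is 79.7%.

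**Sensitivity to a few re-classified participants**

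Section 10.1 judges success by posterior probabilities that the ratio is below 1.0, 0.75, 0.5 and 0.2, under a non-informative prior that it does not specify. We assume independent flat Beta(1,1) priors. With a active and b placebo events out of 70 each, the active rate is Beta(a + 1, 71 − a), the placebo rate is Beta(b + 1, 71 − b), and P(ratio < c) is the probability that the active rate is below c times the placebo rate. Placebo is set at 31 of 70 (0.44 × 70 = 30.8). For active, 0.22 × 70 = 15.4, so the table starts at 16; the lower rows are a weaker-effect case.

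| Active events | Point ratio | P(<1.0) | P(<0.75) | P(<0.5) | Pearson p |
|---|---|---|---|---|---|
| 16 | 16/31 = 0.516 | 0.996 | 0.93 | 0.42 | 0.007 |
| 17 | 17/31 = 0.548 | 0.993 | 0.89 | 0.33 | 0.013 |
| 18 | 18/31 = 0.581 | 0.989 | 0.85 | 0.25 | 0.021 |
| 19 | 19/31 = 0.613 | 0.982 | 0.79 | 0.18 | 0.034 |
| 20 | 20/31 = 0.645 | 0.973 | 0.73 | 0.13 | 0.053 |
| 21 | 21/31 = 0.677 | 0.958 | 0.66 | 0.08 | 0.080 |

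Near the planning rates, one re-classified active participant moves P(<0.5) by about 0.09 and P(<0.75) by 0.03 to 0.04, and leaves P(<1.0) almost unchanged. In the weaker-effect case one participant moves P(<0.75) by about 0.06 and takes an uncorrected Pearson test from 0.034 to 0.053. The protocol's own frequentist analysis is a stratified logistic regression, so that p-value only indicates scale. The table shows sensitivity, not expected bias: the protocol does not say how many participants would qualify through an exacerbation alone.

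**The case against.** The strongest reply is that the protocol discloses the limitation and labels the first analysis interim because of it. It also says that nothing in the trial will be modified on these data. That is fair as disclosure, but it does not stop the log from changing before the final analysis.

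Four stronger readings are tempting, and the protocol does not support them.

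- **The log is cleaned only after unblinding.** Section 10.4.6 lists cleaning before unblinding and does not exclude the log. The later sentence may describe a further clean covering follow-up. What is established is that the log is unlocked at unblinding and frozen afterwards.
- **Two primary results would compete with no rule between them.** The section calls the first analysis interim and the second final, so the later one stands.
- **Site staff would edit entries knowing treatment.** The section does not say that sites are unblinded. Under Appendix 3 the investigator signs eCRF entries, which must agree with source and are verified by monitors. The supported risk is narrower: a sponsor that knows treatment while the log can still be queried and changed.
- **One participant could push the ratio across the 0.5 threshold.** That value is used in a posterior probability and is not a cut-off for the point ratio. At the planning rates the ratio is 0.22/0.44 = 0.50 to begin with, so small moves either side of it carry no meaning.

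Exposure is also limited elsewhere. Section 9.1.5 has the investigator judge loss of control at each clinic visit and indicate which criteria were met. Section 8.1 requires withdrawal from study treatment after an exacerbation, with the reason captured in the eCRF. Where these records sit on visit pages they are frozen, and a later log edit would conflict with them. This narrows the problem for the primary endpoint but does not close it, because the protocol does not say that endpoint status is taken from those pages rather than the log.

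Finally, snapshots and listings of late changes often belong in an analysis or data-management plan, and their absence here is not the complaint. The complaint is the order of events, which the protocol itself sets.

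**Conclusion.** The point holds in a limited form. Followed as written, Section 10.4.6 allows exacerbation entries with onset up to Week 16 to change after treatments are unblinded, and the final primary analysis uses the changed version. For the primary endpoint this touches only participants whose status rests on an exacerbation alone. The exacerbation secondary endpoint depends on the log more directly.

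The effect per participant is gradual: about 0.09 on P(ratio < 0.5) and 0.03 to 0.04 on P(ratio < 0.75) near the planning rates, with no stated decision cut-off to cross. Those sizes rest on the assumed flat priors, 70 evaluable per arm and 31 placebo events. For a Phase IIa proof-of-concept study with the limitation disclosed, this is a cheap improvement and not something that must be fixed.

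**What to change.** Amend Section 10.4.6, with matching data-management wording:

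1. Before unblinding, clean and sign off every exacerbation-log entry with onset on or before the Week 16 or early-withdrawal visit, and take a dated snapshot. An export is enough, so the inability to lock the form is no obstacle.
2. Base the primary endpoint and the exacerbation-based secondary endpoints on that snapshot in both the Week 16 and the final analysis.
3. List any later change to those entries with its reason, and show its effect only as a sensitivity analysis.
4. State that sites and the staff who handle queries stay blinded until the final freeze.

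The cost is a few paragraphs of wording, one data snapshot and a few more days of cleaning before the Week 16 unblinding. Sample size, visits and analysis methods do not change. A genuine late correction to an early event would no longer enter the primary result, but it would remain visible in the listing and the sensitivity analysis.

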12. APPENDICES

12.1. Appendix 1: Abbreviations and Trademarks

Abbreviations

ACQ	Asthma Control Questionnaire	
AE	Adverse Event	
AESI	Adverse Event of Special Interest	
ALT	Alanine Transaminase	
AST	Aspartate Transaminase	
ATS	American Thoracic Society	
AUC	Area Under the Curve	
BID	Twice a day	
BUN	Blood Urea Nitrogen	
CAD	Coronary artery disease	
CI	Confidence Interval	
CV	Cardiovascular	
Cmax	maximum serum concentration	
CIOMS	Council for International Organizations of Medical Sciences	
CONSORT	Consolidated Standards of Reporting Trials	
COPD	Chronic Obstructive Pulmonary Disease	
СРК	Serum creatine phosphokinase	
CSR	Clinical Study Report	
DNA	Deoxyribonucleic acid	
ECG	Electrocardiogram	
(e)CRF	(Electronic) Case Report Form	
ER	Emergency Room	
eDiary	Electronic Diary	
ETP	End of Treatment Phase	
ERS	European Respiratory Society	
EW	Early Withdrawal	
FDA	Food and Drug Administration	
FeNO	Fractional Exhaled Nitric Oxide	
FEV1	Forced expiratory volume in 1 second	
FP	Fluticasone Propionate	
FSH	Follicle Stimulating Hormone	
FTIH	First Time in Human	
FVC	Forced Vital Capacity	
GCP	Good clinical practice	
GCSP	Global Clinical Safety and Pharmacovigilance	
GGT	Gamma-glutamyltransferase	
GINA	Global Initiative for Asthma	
GLI	Global Lung Function Initiative	
GLP	Good laboratory practice	
GSK	GlaxoSmithKline	

HBsAg	hepatitis B surface antigen		
hCG	Human Chorionic Gonadotropin		
HIPAA	Health Insurance Portability and Accountability Act		
HIV	Human Immunodeficiency Virus		
HPLC	High performance liquid chromatography		
HR	Heart rate		
HRT	Heart rate Hormone Replacement Therapy		
IB			
ICF	Investigator's Brochure Informed Consent Form		
ICH	International Conference on Harmonization		
ICS	Inhaled Corticosteroids		
IEC	Independent Ethics Committee		
IgG2σ	human immunoglobulin G2 sigma isotype		
IgG	Immunoglobulin G		
IL-33R	Interleukin-33 receptor		
IL-1RL1	Interleukin-1 receptor like-1		
IP	Investigational Product		
IRB	Institutional Review Board		
iSRC	Independent Safety Review Committee		
IUD	Intrauterine device		
IUS	Intrauterine hormone-releasing system		
IV	Intravenous		
IWRS	Interactive Web Response System		
Kg	Kilogram		
LABA	Long-Acting Beta-2-Agonists		
LTRA	Leukotriene Receptor Antagonist		
mAb	monoclonal antibody		
MAO	Monoamine oxidase		
MedDRA	Medicinal Dictionary for Regulatory Activities		
mcg (µg)	Microgram		
MCH	Mean corpuscular haemoglobin		
MCHC	Mean corpuscular haemoglobin concentration		
MCV	Mean corpuscular volume		
MDI	Metered Dose Inhaler		
mg	Milligram		
min	Minute		
mIU	Milli international units		
mITT	Modified Intent-to-treat		
mL	Milliliter		
μL	Microlitre		
mm	Millimeter		
mV	Millivolt		
MSDS	Material Safety Data Sheet		
msec	Millisecond		
NOAEL	No Observed Adverse Effect Level		
NT-proBNP	N-terminal prohormone of brain natriuretic peptide		

NYHA	New York Heart Association
OCS	Oral Corticosteroid
PEF	Peak Expiratory Flow
PD	Pharmacodynamic
PGx	Pharmacogenetic
PK	Pharmacokinetic
prn	As needed
PSVT	Paroxysmal supraventricular tachycardia
q2W	Every two weeks
QTc	QT interval corrected for heart rate
QTcB	QT interval corrected for heart rate by Bazett's formula
QTcF	QT interval corrected for heart rate by Fridericia's formula
RBC	Red Blood Cell
RDW	Red cell distribution width
RNA	Ribonucleic acid
SABA	Short-Acting Beta-2-Agonists
SAD	Single Ascending Dose
SAE	Serious Adverse Event
Sal	Salmeterol
SGPT	Serum Glutamic-Oxaloacetic Transaminase
SGRQ	St. George's Respiratory Questionnaire
SRM	Study Reference Manual
ST2	Suppressor of tumorigenicity 2
sST2	Soluble ST2
ULN	Upper Limit of Normal
US	United States
VT	Ventricular Tachycardia
WBC	White Blood Cell
WOCBP	Woman of childbearing potential
W/V	Weight/volume

Trademark Information

Trademarks of the GlaxoSmithKline group of companies
DISKUS

Trademarks not owned by the GlaxoSmithKline group of companies	
None	

12.2. Appendix 2: Clinical Laboratory Tests

- The tests detailed in Table 5 will be performed by the central laboratory.
- All protocol required laboratory assessments (haematology, clinical chemistry and urinalysis) must be conducted in accordance with the Laboratory Manual and the SoA. Laboratory requisition forms must be completed and samples must be clearly labelled with the participant number, protocol number, site/centre number, and visit date. Details for the preparation and shipment of samples will be provided by the laboratory and are detailed in the Laboratory Manual. Reference for all safety parameters will be provided to the site by the laboratory responsible for the assessments.
- All blood samples which will be taken pre-dose, will be sent to a central laboratory for analysis (details provided in the Laboratory Manual). Standard reference ranges will be used.
- If additional non-protocol specified laboratory assessments are performed at the institution's local laboratory and result in a change in participant management or are considered clinically significant by the Investigator (e.g., SAE or AE or dose modification) the results must be recorded in the eCRF.
- Refer to the Laboratory Manual for appropriate processing and handling of samples to avoid duplicate and/or additional blood draws.
- Protocol-specific requirements for inclusion or exclusion of participants are detailed in Section 6 of the protocol.
- Additional tests may be performed at any time during the study as determined necessary by the investigator or required by local regulations.

Table 5 Protocol-Required Safety Laboratory Assessments

Laboratory Assessments	Parameters					
Hematology	Platelet Count Red Blood Cell (RE Count Hemoglobin Hematocrit White Cell Count RDW	BC)	RBC Indices MCV MCH MCHC	3:	WBC count with Neutrophils Lymphocytes Monocytes Eosinophils Basophils These will be blir onwards.	
Clinical Chemistry ¹	BUN	Potas	ssium	Ar (A GI O: Tr	spartate minotransferase ST)/ Serum lutamic- xaloacetic ransaminase GOT)	Total and direct bilirubin

Laboratory Assessments	Parameters			
	Creatinine	Sodium	Alanine Aminotransferase (ALT)/ Serum Glutamic-Pyruvic Transaminase (SGPT)	Total Protein
	Glucose nonfasting	Calcium	Alkaline phosphatase	CPK
	Albumin	Phosphorus Carbon Dioxide	GGT	Chloride
Cardiac Markers Routine Urinalysis	 Cardiac troponin I (cTn I) N-terminal pro-brain natriuretic peptide (NT-proBNP) Specific gravity pH, glucose, protein, blood, ketones, bilirubin, leukocyte, nitrite, urobilinogen by dipstick 			
	Microscopic examination (if blood or protein is abnormal)			
Other Screening Tests	Follicle-stimulating hormone and estradiol (as needed in women of non-childbearing potential only) Serum/urine human chorionic gonadetropin (hCG) pregnancy test (as			
	 Serum/urine human chorionic gonadotropin (hCG) pregnancy test (as needed for women of childbearing potential)² 			
	Serology (HIV antibody, hepatitis B surface antigen HBsAg, and hepatitis C virus antibody)			
	"All study-required laboratory assessments will be performed by a central laboratory.			

NOTES:

- 1. Details of liver chemistry stopping criteria and required actions and follow-up assessments after liver stopping or monitoring event are given in Section 8.1 and Appendix 7. All events of ALT ≥3 × upper limit of normal (ULN) and bilirubin ≥2 × ULN (>35% direct bilirubin) or ALT ≥3 × ULN and international normalized ratio (INR) >1.5, if INR measured, which may indicate severe liver injury (possible Hy's Law), must be reported as an SAE (excluding studies of hepatic impairment or cirrhosis).
- Local urine testing will be standard for the protocol unless serum testing is required by local regulation or IRB/IEC.
 Abbreviations: RBC= Red Blood Cell Count, WBC= White Blood Cell Count, MCV= Mean corpuscular volume,
 MCH= mean corpuscular haemoglobin, MCHC= mean corpuscular haemoglobin concentration, RDW= Red cell
 distribution width, AST= Aspartate Aminotransferase, ALT= Alanine Aminotransferase, SGPT= Serum Glutamic Oxaloacetic Transaminase, CPK= creatine phosphokinase, GGT= Gamma-glutamyltransferase, hCG= human
 chorionic gonadotropin, HIV= Human Immunodeficiency Virus

